STUDY SYNOPSIS**NCT03926819****Date: January 30, 2023**

Title of Study: A Phase 1 ascending single-dose followed by multiple dose safety and pharmacokinetic study of HBI-002 carbon monoxide liquid formulation in healthy adult volunteers.
Protocol Number: HBI-002-001
Investigators/Study Center:
Phase of Development: 1
Objectives/Endpoints: Primary Objective/Endpoint: To assess the safety and tolerability of HBI-002, given as single ascending doses (SAD) and multiple doses (MD) daily for 7 days in healthy male and female adult subjects based on frequency and severity of TEAE, including adverse events of special interest. Secondary Objectives/Endpoints: 
1. To evaluate the pharmacokinetics (PK) of HBI-002 with increasing doses of oral HBI-002 as measured by COHb levels.2. To determine the HBI-002 dose required to achieve peak COHb levels up to 10% within one hour after ingestion.3. To evaluate any accumulation of CO as measured by COHb with daily dosing and to assess changes in venous lactate levels.4. To evaluate biomarkers of inflammation and to assess changes induced by HBI-002.
Planned Sample Size: Up to 16 subjects will be enrolled in the SAD phase (up to 4 dose cohorts) and 4 subjects in the MD phase (one dose cohort). Additional subjects (up to 8 in the SAD phase and up to 6 in the MD phase) may be enrolled in any cohort, as needed, if incomplete data is obtained or there is a need to obtain additional safety observations. Subjects in the MD cohort will be replaced if all 7 doses are not ingested or labs for safety assessment are not complete. Subjects will not be replaced in the event the subject discontinues the study due to a related adverse event.
Study Duration: Approximately 26 weeks
Study Design: This is a single center, open-label trial investigating up to four single ascending doses (SAD), followed by a single cohort of multiple doses (MD) with dosing daily for 7 days. Both the SAD and MD dosing cohorts utilize an adaptive dosing regimen. Eligible healthy adult subjects who have signed the informed consent will undergo a screening assessment carried out within 4 weeks of study entry consisting of a medical history, concomitant medications, physical examination, height and weight, vital signs, ECG, hematology and chemistry labs, infectious disease screen including SARS-CoV-2, hemoglobin electrophoresis, urinalysis, pregnancy and drug screen. Pregnancy testing in females of childbearing potential will be carried out in both the SAD and MD study components at screening and baseline, as well as in the SAD component at 48 hours and on Day 30, and in the MD component on Days 8 and 37. Concomitant medications and adverse events will continue to be monitored to the final follow up visit.
Dosing rules (SAD and MD) For the SAD study component, there will be at least 72 hours between dosing of the first study subject at each dose level and the subsequent 3 subjects at the same dose level and with no minimum time between dosing of each subsequent subject. There also will be at least 72 hours between the last subject at each dosing level and the first subject at the next dose level. For the MD study component,

there will be at least 30 days between the last subject at the final SAD dose level and the first subject in the MD dose level. For the MD dosing, there will be 72 hours between the first subject receiving the first MD dose and the subsequent 3 subjects at that dose level with no minimum time between dosing of the 3 subsequent subjects.

All subjects (SAD and MD)

Peak COHb measured by co-oximeter will be monitored for safety, targeting levels of no more than 10% COHb, and COHb saturation will be documented for each subject at all time points. The DSMB will review safety information through 72 hours after completion of dosing for each SAD cohort. The specific dose cohort at the next level, as designated under SAD dosing, may proceed provided that no related safety issues are observed.

The DSMB will review safety information after completion of dosing for all SAD cohorts at 30 days post-dosing of the final subject in the final SAD cohort. The safety and PK data from the SAD phase will be submitted to the FDA prior to the initiation of the MD phase. The MD phase will not be initiated until the FDA has approved of the advancement.

COHb measured by co-oximeter and venous lactate together with pH measurements will be carried out and reported within one hour of the respective blood draw for all study subjects. COHb, pH and lactate results will be provided to the PI and MM as soon as available, but not later than one hour after the respective blood draw.

Subjects will be released when all of the following criteria have been met.

1. COHb saturation by venous blood gas, venous lactate and pH at normal physiological levels.
2. Transcutaneous oxygen saturation at normal physiological level.
3. Normal vital signs and cardiac rhythm.
4. No adverse symptomatology.

Subjects demonstrating clinical or laboratory abnormalities at the designated final visit will continue to be followed until the abnormality is resolved or stabilized.

Stopping Rules

If any subject experiences signs or symptoms of CO toxicity as detailed below, further enrollment and dosing will be put on hold until the DSMB reviews relevant data and makes recommendations as to next steps. In addition, for the affected subject(s), that subject(s) will be discontinued and will immediately be administered oxygen. If the protocol is put on hold for any reason, Hillhurst will communicate DSMB recommendations to FDA before resuming enrollment.

Subjects will not be replaced if they discontinue the study due to an adverse event (AE).

Diagnosis and Key Subject Selection Criteria: Subjects who satisfy all of the inclusion and exclusion criteria below will be eligible to participate in the study.

Inclusion Criteria

1. Signed informed consent.
2. Healthy male or female 18-55 years of age inclusive.
3. Negative HBsAg, aHCV, aHIV, and SARS-CoV-2 test.
4. Non-smoker or vaper (no use of tobacco or marijuana products within 3 months of screening).
5. Body weight between 60 kg and 110 kg (inclusive) and with BMI less than 30 kg/m².
6. Subjects must be healthy as defined by:
 - a. absence of clinically significant hematological, renal, endocrine, pulmonary, gastrointestinal, cardiovascular, hepatic, psychiatric, neurologic or allergic disease, as determined by the Investigator.
 - b. liver function: alanine transaminase (ALT) and aspartate transaminase (AST) ≤ 2 times the upper limit of the normal range

- c. total bilirubin \leq 1.5 times the upper limit of the normal range
- d. renal function: creatinine clearance within normal range as assessed by Cockcroft and Gault calculation
- e. carboxyhemoglobin level by venous blood gas \leq 3.5% (any time prior to the first dose)
- f. venous lactate level $<$ 2.0 mmol/L at baseline.
- g. the absence of current clinically relevant abnormalities identified by a detailed medical history, full physical examination including blood pressure and pulse rate measurement, 12-lead ECG, and clinical laboratory tests (hematology and clinical chemistries), as determined by the Investigator.

7. Negative pregnancy tests for females.
8. Subjects must be willing to use a highly effective method of contraception for the duration of the study and for 30 days thereafter.
 - a. Male subjects, without a vasectomy, must use a condom and be instructed that their female partner should use another form of contraception such as an IUD, diaphragm with spermicide, oral contraceptive, injectable progesterone, subdermal implant or a tubal ligation if the female partner could become pregnant
 - b. Female subjects of childbearing potential (not surgically sterilized and less than one year post-menopausal) should use a form of contraception such as an IUD, diaphragm with spermicide, oral contraceptive, injectable progesterone, subdermal implant or a tubal ligation, and be instructed that their male partners should use a condom, if not vasectomized.

Exclusion Criteria

Subjects who meet any of the following criteria will be ineligible for participation in the study:

1. Subjects with concurrent illness/disease as defined by:
 - a. clinically significant hematological, renal, endocrine, pulmonary, gastrointestinal, cardiovascular, hepatic, psychiatric, neurologic or allergic disease, as determined by the Investigator.
 - b. current clinically relevant abnormalities identified by a detailed medical history, full physical examination including blood pressure and pulse rate measurement, 12-lead ECG, and clinical laboratory tests (hematology, clinical chemistries and urinalysis), as determined by the Investigator.
 - c. clinically significant illness and/or surgery within 4 weeks prior to dosing.
2. Anemia of any cause.
3. Homozygous or heterozygous hemoglobinopathy.
4. Blood transfusion within six weeks prior to the first administration of study drug.
5. Carboxyhemoglobin \geq 3.5% (any time prior to the first dose)
6. Oxygen saturation by transcutaneous measurement consistently \leq 95% (any time prior to the first dose)
7. Exposure to any live vaccine within 28 days prior to study drug administration.
8. History of febrile or infective illness within 14 days prior to dosing.
9. Positive pregnancy test or breast feeding for females.
10. Weight loss or gain of more than 5 kg within 3 months prior to dosing.
11. History of alcohol abuse or dependence or regular use of alcohol within six months prior to dosing (defined as more than 14 units of alcohol per week; 1 Unit= 150 mL wine, 360 mL beer or 45 mL of 40% alcohol)
12. Positive result on alcohol screen
13. History of pulmonary infiltrate or pneumonia within 6 months prior to dosing or pulmonary/bronchial infection within 2 weeks prior to dosing.
14. History of cancer, with the exception of adequately treated basal cell or squamous cell carcinoma of the skin more than 1 year prior.
15. History of cardiac disease
16. History of drug abuse or dependence.

17. Positive results on drug screen (oxycodone, benzodiazepines, THC, cocaine, opiates, and methamphetamine).
18. Use of prescription drugs within 7 days or 5 half-lives (whichever is longer) prior to dosing. Herbal and vitamin supplements must be discontinued 14 days prior to dosing.
19. Unwilling or unable to comply with the requirements of the protocol.
20. Treatment with an investigational drug within the longer of 30 days or five half-lives.
21. Systolic blood pressure lower than 90 or above 140 mm Hg, diastolic blood pressure lower than 50 or above 90 mm Hg, heart rate less than 45 or above 100 bpm, or arrhythmia at screening and/or baseline. ECG abnormalities or other vital sign abnormalities that are clinically significant at screening and/or baseline, as determined by the Investigator.
22. Other severe acute or chronic medical or psychiatric condition or laboratory abnormality that may increase the risk associated with study participation or investigational product administration or may interfere with the interpretation of study results and, in the judgment of the investigator, would make the subject inappropriate for entry into the study.
23. History of allergic reactions to any of the drug product excipients
24. History of epilepsy or seizure
25. History of suicide attempts or ideation (by medical history)

Criteria for Evaluation/Statistical Methods:**Pharmacokinetics:**

PK will be assessed in each subject based on whole blood COHb levels obtained at each designated blood draw. PK will be assessed on each subject in the SAD phase and on each subject in the MD phase with COHb. In the MD phase, PK analysis will be carried out on both the first and final dose of HBI-002. Standard pharmacokinetic parameters for COHb incremental recovery [IR], maximum concentration following oral administration [Cmax], time to reach Cmax [Tmax], terminal or disposition half-life [$t_{1/2}$], mean residence time [MRT], systemic clearance [Cl/F], area under the whole blood-time curve [AUC] and volume of distribution [Vd/F] after single oral administrations of HBI-002 at each dose level. The PK concentration data at each timepoint will be listed for each subject and summarized by dose level using descriptive statistics. Individual subject and mean concentration-time data will be graphically presented separately. If sufficient data are available across SAD dose cohorts, dose proportionality will be evaluated using a power model.

PK analyses will use the actual observed sample drawing times. Samples with unknown drawing time and/or where the concentration could not be determined will be eliminated from the calculations. Concentration data will be carried out in two modes: No correction for baseline value and corrected for baseline by subtraction of the mean pre-dosing value.

PK parameters will be derived using noncompartmental methods with appropriate software. The following parameters will be calculated for each patient separately: AUC, IR, Cmax, AUCinf, Tmax, $t_{1/2}$, MRT, Clearance (CL/F) and Vd/F. These parameters will be summarized for each Dose Cohort separately by using descriptive statistics (number, mean, standard deviation, minimum, maximum, median, coefficient of variation, geometric mean and the corresponding 90% confidence intervals as appropriate).

Safety:

All safety data will be included in the subject data listings. Summary tables will be based upon the safety population.

Serious and non-serious adverse events, occurring up to 30 days after the last oral dose will be tabulated and summarized according to the most recent version of the MedDRA. Frequencies and percentages of subjects experiencing at least one event will be summarized by system organ class and preferred term for all AEs, for AEs considered to be possibly or probably related to the study drug, and for SAEs. The number and proportion of subjects experiencing these events will be tabulated by dose for each study phase (SAD or MD). Related adverse events will be listed.

Individual and summary vital signs and clinical laboratory data will be presented for each study phase in tabular form with mean, standard deviation and range as appropriate.

For the vital signs, transcutaneous oxygen concentration, venous COHb and other laboratory safety data, and ECG data, out of range values considered to be clinically significant will be flagged in the data listings and a separate listing of clinically significant abnormal values will be presented, including any COHb value >10%.

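### The only SARS-CoV-2 test placed in the synopsis is at screening, up to 4 weeks before study entry, so a qualifying negative says little about infection at dosing (minor; cheap to fix).

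*Combined protocol and SAP*

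**What the plan says.** The Study Design section says that eligible subjects "undergo a screening assessment carried out within 4 weeks of study entry". The content of that assessment includes an "infectious disease screen including SARS-CoV-2, hemoglobin electrophoresis, urinalysis, pregnancy and drug screen". This is the only visit to which the supplied text assigns the SARS-CoV-2 test.

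Inclusion criterion 3 requires a "Negative HBsAg, aHCV, aHIV, and SARS-CoV-2 test" and gives no date limit and no repeat.

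Other checks are tied more closely to dosing:

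- Pregnancy testing "will be carried out in both the SAD and MD study components at screening and baseline".
- Lactate is a baseline criterion (inclusion 6f).
- COHb and oxygen saturation apply at any point up to the first dose (inclusion 6e, exclusions 5 and 6).
- Vital signs and ECG are judged at screening and/or baseline (exclusion 21).

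Three exclusions on illness are also timed to dosing. Exclusion 1c covers clinically significant illness in the preceding 4 weeks. Exclusion 8 covers "History of febrile or infective illness within 14 days prior to dosing". Exclusion 13 includes "pulmonary/bronchial infection within 2 weeks prior to dosing".

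**The concern.** SARS-CoV-2 status can change within days, so a negative result several weeks old is weak evidence about status at dosing. Exclusions 1c, 8 and 13 work through illness that someone has noticed, and the oxygen-saturation rule needs readings that are consistently low. A subject with an asymptomatic or unrecognised infection can pass all of them with a negative test from the start of the screening window.

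Two analyses are exposed. The primary endpoint is the frequency and severity of TEAEs, and the Safety section tabulates all events as well as related ones, so symptoms of an infection enter the all-event tables however they are attributed. Secondary objective 4 looks for biomarker changes caused by HBI-002 in an open-label trial with no control group described. A change from baseline driven by infection would have no comparator to reveal it, and a biomarker value has no relatedness assessment. The second exposure is the more serious.

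**Working it through.** The plan states no infection rate and no related probability, so there is no figure to reproduce. The timing point follows from reading Study Design and inclusion 3 together. The arithmetic below only illustrates its size.

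**Inputs from the documents**

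- Longest gap from test to study entry: 4 weeks = 28 days. Study entry is not defined as the day of dosing; I take it as that day.
- Planned subjects: 16 (SAD) + 4 (MD) = 20.
- Cohort size: 4, so one subject is 1/4 = 25% of a cohort, or 1/16 = 6.3% of the SAD phase.

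**Assumptions, not in the documents**

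- Weekly infection rate *i*: 0.25% to 1%, constant and independent between subjects.
- An infection still matters at dosing only if acquired in the last 10 days (used in the middle column).
- The test finds every infection present when it is taken.

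**Formulas**

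- Per subject, over *d* days: p = 1 − (1 − i)^(d/7).
- At least one of 20: P = 1 − (1 − p)^20 = 1 − (1 − i)^(20d/7).

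The exponent 20d/7 is 80 for 28 days, 28.57 for 10 days and 8.57 for 3 days.

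| Weekly rate | 28-day gap, all infections counted | 28-day gap, last 10 days only | 72-hour gap |
|---|---|---|---|
| 0.25% | 1 − 0.9975^80 = 18.1% | 1 − 0.9975^28.57 = 6.9% | 1 − 0.9975^8.57 = 2.1% |
| 0.5% | 1 − 0.995^80 = 33.0% | 1 − 0.995^28.57 = 13.3% | 1 − 0.995^8.57 = 4.2% |
| 1% | 1 − 0.99^80 = 55.2% | 1 − 0.99^28.57 = 25.0% | 1 − 0.99^8.57 = 8.3% |

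**Reading the table**

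- The first column is an upper bound. It gives every subject the longest permitted gap and counts infections that resolved, or were recognised and excluded, before dosing. With a 14-day gap for everyone (exponent 40) the range is 9.5% to 33%.
- The middle column is closer to what matters at dosing, and is still about three times the 72-hour column.
- The 72-hour column is somewhat optimistic, because a test can miss an infection acquired shortly before it.

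**What a pre-dose test leaves untouched.** AEs are tabulated up to 30 days after the last dose. At the same assumed rates, the chance that at least one of 20 subjects is infected over 30 days (exponent 20 × 30/7 = 85.7) is 1 − 0.9975^85.7 = 19% to 1 − 0.99^85.7 = 58%. The timing of the entry test has no effect on this.

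**The case against.** The strongest reply is that the text is a synopsis. It has no schedule of assessments and does not list the content of the baseline visit. The screening list is visibly incomplete: it omits COHb, lactate, oxygen saturation and the alcohol screen, all of which the eligibility criteria require. Silence about a check-in test does not prove that none is done. This stands, so the point is confined to the text supplied. It does not supply the time limit that inclusion 3 lacks.

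A second reply is that a test up to 72 hours before dosing can miss the most recent infections, and that infection during follow-up is at least as likely. Both are true. They limit what the change achieves, but the part of the gap between screening and check-in would still be closed.

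A reader might infer that an incubating infection would be read as an HBI-002 effect. The documents do not support that. The Safety section separates events considered possibly or probably related from all events, escalation depends on related safety issues, and the DSMB reviews the data. A reader might also infer that infection symptoms would trigger the hold in the Stopping Rules. That cannot be checked, because the list of CO-toxicity signs to which the rule points is not in the supplied text.

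**Conclusion.** The point holds as a minor one. As written, a SARS-CoV-2 negative up to 28 days old meets inclusion 3, and the illness exclusions do not cover unrecognised infection. One affected subject is a quarter of a cohort. The likely consequence is noise in the all-event TEAE tables and, with less protection, in the uncontrolled biomarker changes.

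The 18% to 55% range should not be taken as the probability that results are confounded. It is a ceiling on an assumed infection rate. The gain from testing near dosing is better judged by comparing about 7% to 25% with about 2% to 8%, which rests on the assumed weekly rate, the assumed 10-day window and the assumed perfect test. The direction does not depend on the rate: for any positive rate, the shorter gap gives the smaller chance.

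**What to change.** In Study Design and inclusion criterion 3, require the negative SARS-CoV-2 result to be obtained at baseline/check-in, for example within 72 hours before the first dose, instead of at any time in the 4-week screening window. The other screening tests need not move on this argument.

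This moves an existing test and adds none. The cost is protocol wording and an occasional late exclusion at check-in, after other screening costs have been spent. If a full schedule of assessments already requires a test near dosing, one clause in the synopsis and in inclusion 3 is enough.

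The change does not cover very early incubation or infection acquired after dosing starts.

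### With no minimum interval between the three post-sentinel subjects, in SAD or MD, all three may be dosed before any of their COHb results can be acted on

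*Combined protocol and SAP*

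**What the plan says.** All references are to the Study Synopsis in the combined protocol and SAP.

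- **Spacing (Study Design, Dosing rules).** At each SAD level the first subject is dosed at least 72 hours before the other three, who then have "no minimum time between dosing of each subsequent subject". The MD cohort has the same 72-hour lead and then "no minimum time between dosing of the 3 subsequent subjects".
- **Results (Study Design, All subjects).** COHb, pH and lactate reach the PI and MM no later than one hour after each draw.
- **Hold (Study Design, Stopping Rules).** The trigger is worded as follows: "If any subject experiences signs or symptoms of CO toxicity as detailed below, further enrollment and dosing will be put on hold". The hold lasts while the DSMB considers the data. The affected subject is discontinued and given oxygen.
- **Progression (Study Design, All subjects).** The DSMB reviews each SAD cohort through 72 hours, and the next level may proceed if there are no related safety issues. MD needs a 30-day DSMB review, submission of the SAD data and FDA approval.
- **The 10% figure.** It is part of secondary objective 2 ("To determine the HBI-002 dose required to achieve peak COHb levels up to 10% within one hour after ingestion"), a monitoring target ("Peak COHb measured by co-oximeter will be monitored for safety, targeting levels of no more than 10% COHb"), and, under Safety, the cut-off for inclusion in the listing of clinically significant values.
- **Adaptation.** "Both the SAD and MD dosing cohorts utilize an adaptive dosing regimen", but the supplied text does not give the rules.

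**The concern.** A hold helps only subjects who have not yet been dosed. The sentinel gap gives 72 hours to act on the first subject. After that, the plan allows the other three to be dosed together. If one of them has a high COHb or early symptoms, the other two may already have taken the same dose. This applies whatever triggers the hold, so it does not depend on whether a COHb threshold exists.

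The one-hour reporting rule produces the information needed for a decision between subjects, but the dosing rule does not require anyone to wait for it. What is at stake is avoidable exposure of healthy volunteers, mainly in cohorts whose peaks come near the 10% that secondary objective 2 explores.

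**Working it through.** **1. Cohort structure.** The plan's SAD total is reproduced by 4 cohorts × (1 sentinel + 3) = 16. Three subjects per cohort fall under the rule with no minimum time.

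**2. Interval needed.** Interval = time to peak draw + time to result. Reporting takes at most 1 hour (Study Design). The peak is assumed to be drawn at 1 hour, from the intention in secondary objective 2; it is not an observed Tmax, and the sampling times are not supplied.

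- Peak at 1 h: 1 + 1 = 2 h; two gaps = 4 h per cohort.
- Peak at 0.5 h: 1.5 h; two gaps = 3 h.
- Peak at 2 h: 3 h; two gaps = 6 h.

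The plan's minimum is 0 h.

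**3. Size of the benefit.** The documents give no cohort medians and no CV, so both are assumed. Peaks are taken as lognormal and independent between subjects, with dosing paused at the first post-sentinel value above 10%.

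- σ = √ln(1 + CV²); for CV 20%, σ = 0.198.
- p = P(peak > 10%) = 1 − Φ(ln(10/median)/σ).
- Spacing avoids at least one exceedance when the sentinel is at or below 10% and at least two of the next three would exceed it: (1 − p)[3p²(1 − p) + p³].
- Expected exceedances avoided: (1 − p)[3p − (1 − (1 − p)³)].
- Chance that a cohort of four has any value above 10%: 1 − (1 − p)⁴.

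Example, median 8%, CV 20%: ln(10/8)/0.198 = 1.127, so p = 0.130. Chance of avoiding at least one: 0.870 × [3 × 0.130² × 0.870 + 0.130³] = 0.040. Any value above 10% among four: 1 − 0.870⁴ = 0.43.

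| Median peak (CV 20%) | p | At least one avoided | Expected avoided | Any above 10% in four |
|---|---|---|---|---|
| 7% | 0.036 | 0.4% | 0.004 | 14% |
| 8% | 0.130 | 4% | 0.04 | 43% |
| 9% | 0.297 | 15% | 0.17 | 76% |
| 10% | 0.500 | 25% | 0.31 | 94% |

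For medians of 7, 8, 9 and 10%, the chance of avoiding at least one is 0.02, 1, 11 and 25% with CV 15%, and 3, 10, 19 and 25% with CV 30%. At a median of 6% it is 0.5% or less throughout.

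Under these assumptions the avoided-exceedance figures are upper bounds. They suppose that a paused subject is never dosed at that level, and that without spacing all three would be dosed before any result. Cohorts whose sentinel exceeds 10% are not counted, because the 72-hour gap already allows action.

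**4. COHb triggers in the supplied text.** Hold and discontinuation turn on signs or symptoms, and progression turns on related safety issues. COHb governs eligibility (3.5%) and release (normal levels), which are neither holds nor progression decisions. No supplied rule ties a COHb value to a hold, a discontinuation or progression. Three places where one could stand are not supplied: the toxicity list to which the stopping rule points, the adaptive dosing rules, and the SAD dosing section.

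**The case against.** The safeguards are real: a 72-hour sentinel in every cohort, DSMB review of each SAD cohort, release only at normal COHb, and FDA approval before MD. With daily dosing, the MD sentinel will have had about three doses before the others start. The absence of a minimum time permits simultaneous dosing but does not require it, and the site may stagger subjects anyway. The 2 hours rests on an objective and not on an observed Tmax. All this limits the size of the point, but none of it makes the interval part of the rule.

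A reader might infer more: that the trial has no COHb stopping criterion, and that a symptom-free value above 10% would not change dosing. The documents do not support that. The text is a synopsis, and the three places most likely to hold such a criterion are not supplied. An adaptive regimen serving secondary objective 2 could hardly ignore COHb, and the DSMB could treat a high value as a related safety issue.

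A reader might also infer that 10% should be a stopping limit. The study aims for peaks up to 10%. At an assumed median of 8% and 20% CV, about 43% of cohorts would trigger such a pause, to avoid at most 0.04 exceedances per cohort on average. The documents show no harm from a brief symptom-free value above 10%. Finally, calling the wait a pause may not settle whether it is a hold, given the FDA communication required "If the protocol is put on hold for any reason". These objections stand and limit the point to spacing and to stating or citing a threshold.

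**Conclusion.** The point holds for spacing. In both SAD and MD, the stated rule lets all three post-sentinel subjects be dosed before any of their COHb results or early symptoms could trigger even the existing hold. This follows from the text alone and needs no assumption about COHb variability.

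The size does rest on assumptions. With 20% CV, the chance per cohort of avoiding a further value above 10% is at most 4% at a median of 8% and 15% at 9%, and it is negligible at 6%. No probability is claimed for MD accumulation. Symptoms that appear after the interval would not be caught by it.

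On a COHb action threshold, the documents allow only a conditional conclusion: none is shown, and whether the full plan has one cannot be told from the supplied text. This is a cheap improvement, with medium confidence.

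**What to change.** 1. **Spacing.** In the Dosing rules for SAD and MD, replace the absence of a minimum time with about 2 hours between post-sentinel subjects, lengthened if the observed Tmax is later. Require the investigator to review the previous subject's COHb result before the next subject is dosed.
2. **Threshold.** If the toxicity list, adaptive dosing rules or SAD dosing section contain a COHb criterion, cite it in the Stopping Rules; it governs. If not, the sponsor and DSMB should set an action threshold, not necessarily 10%, at which the next dose waits for review. State whether that wait counts as a protocol hold. State also whether a withheld MD dose leads to replacement, since "Subjects in the MD cohort will be replaced if all 7 doses are not ingested".

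**Cost.** Wording, plus about 4 hours per cohort (3 to 6 hours if the peak is at 0.5 to 2 hours). In MD the stagger recurs on each dosing day if subjects keep a 24-hour interval. A threshold adds DSMB contacts, more often the closer it lies to the cohort median. With a 2-hour result, advice is needed within 24 − 2 = 22 hours if the next daily MD dose is not to be delayed or missed.

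### Exclusion 4 bars recent blood transfusion but no criterion bars recent blood donation, which can raise the COHb response modestly; this matters only near the 10% target (low severity)

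*Combined protocol and SAP*

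**What the plan says.** Three adjacent items under Exclusion Criteria concern hemoglobin: item 2 ("Anemia of any cause"), item 3 (hemoglobinopathy) and item 4 ("Blood transfusion within six weeks prior to the first administration of study drug"). No hemoglobin cut-off is given. Donation and phlebotomy are not named in any inclusion or exclusion criterion. Blood loss is touched only indirectly, through item 1c: "clinically significant illness and/or surgery within 4 weeks prior to dosing".

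COHb has three roles in this trial:

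- **Safety target** (Study Design, All subjects): "Peak COHb measured by co-oximeter will be monitored for safety, targeting levels of no more than 10% COHb". The Safety part of the statistical methods also lists clinically significant abnormal values, "including any COHb value >10" percent.
- **Dose finding** (secondary objective 2): "To determine the HBI-002 dose required to achieve peak COHb levels up to 10% within one hour after ingestion".
- **Pharmacokinetics** (statistical methods): "PK will be assessed in each subject based on whole blood COHb levels".

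**The concern.** COHb is a percentage of hemoglobin. With less hemoglobin in circulation, the same absorbed CO occupies a larger share of it. The protocol already treats hemoglobin as an eligibility matter, yet donation acts on the same quantity and is left open.

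The nearby criteria need not close the gap. Item 2 requires anemia. Item 1b requires an abnormality the investigator judges relevant. Item 22 requires a condition or laboratory abnormality judged to raise risk or to interfere with interpretation. A donor whose hemoglobin has fallen but is still normal can pass all three. Screening may also take place up to 4 weeks before entry, and the text does not address a donation made after the screening sample.

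The trial looks for a dose whose peak comes close to its own 10% target, so headroom at the top dose is small by design. A donor there could exceed the target for a reason unrelated to the dose step.

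**Working it through.** The plan states no figure on this point, so there is none to reproduce. What follows is a sensitivity calculation.

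**Inputs from the documents:** body weight 60 to 110 kg (inclusion 5); baseline COHb effectively below 3.5% (inclusion 6e with exclusion 5); target of no more than 10%; 4 subjects per cohort.

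**Assumptions:** donation D = 450 to 500 mL, with the lost hemoglobin not yet replaced; blood volume V = 65 to 75 mL/kg; all absorbed CO bound to hemoglobin; equal absorption in donors and non-donors.

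**Step 1. Hemoglobin lost and size of the rise.** Lost fraction f = D / (weight × V). The COHb rise is multiplied by m = 1/(1 − f).

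- 60 kg: f = 450/4500 = 0.100 to 500/3900 = 0.128, so m = 1.111 to 1.147.
- 110 kg: f = 450/8250 = 0.055 to 500/7150 = 0.070, so m = 1.058 to 1.075.
- If half the loss has been replaced at 60 kg: f = 0.050 to 0.064, so m = 1.053 to 1.068.

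**Step 2. Peak in a donor.** If a non-donor goes from baseline b to peak T, the donor peaks at b + (T − b) × m. With b = 1%:

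| Non-donor peak T | 110 kg (m = 1.058 to 1.075) | 60 kg (m = 1.111 to 1.147) |
|---|---|---|
| 8% | 8.4% to 8.5% | 8.8% to 9.0% |
| 9% | 9.5% to 9.6% | 9.9% to 10.2% |
| 10% | 10.5% to 10.7% | 11.0% to 11.3% |

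The excess is (T − b) × (m − 1). For T from 8% to 10% and b from 0.5% to 3.4%, it runs from (8 − 3.4) × 0.058 = 0.3 to (10 − 0.5) × 0.147 = 1.4 percentage points.

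**Step 3. When 10% is crossed.** The loss needed is f = 1 − (T − b)/(10 − b). With b = 1%, that is 5.6% at T = 9.5%, 11.1% at T = 9% and 22.2% at T = 8%. The last lies well beyond the largest f in step 1. Solved for T at the largest loss (f = 0.128), the crossing point is b + (10 − b) × 0.872, which is 8.8% for b = 0.5% and 9.2% for b = 3.4%.

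**Step 4. Effect on a 4-subject geometric mean with one donor.** The baseline-corrected mean is multiplied by the fourth root of m, that is 1.014 to 1.035. Without baseline correction, taking a 1.5% baseline and an 8-point rise (peak 9.5%), the factor is the fourth root of (1.5 + 8m)/9.5, that is 1.012 to 1.030. For scale, assume a between-subject CV of 15% to 30%. The upper 90% confidence limit for a geometric mean with n = 4 then lies about 19% to 41% above the estimate.

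**The case against.** The case against acting has four parts.

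**Other criteria already cover much of this.** Exclusion 20 bars an investigational drug within the longer of 30 days or five half-lives, which removes most volunteers bled in an earlier drug study. Item 1c covers surgical loss within 4 weeks. This stands, and it narrows the gap mainly to voluntary donation by someone who is not anemic. A reader might infer that blood loss is wholly unrestricted; the documents do not support that.

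**Permitted weight variation is larger.** At a fixed mL/kg, 60 to 110 kg is a 110/60 = 1.83-fold range in blood volume, against at most 1.15-fold from donation. The text available does not say whether dose is scaled to weight. A non-donor with the same hemoglobin mass would still be admitted. This limits the benefit, but donation adds to the spread at any given weight and can be removed with one question.

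**The PK effect is negligible.** This stands. A shift of about 1% to 3.5% in one cohort mean would not be discernible at n = 4, and the power model is itself conditional on sufficient data.

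**Monitoring limits the consequence.** COHb is reported within one hour of each draw, 72 hours separate the first subject from the next three, and the DSMB reviews each SAD cohort. These measures detect a high value but do not prevent it. The three later subjects have no minimum interval between them, so a first subject who is not a donor gives no warning about a later one who is.

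Two further readings go too far. One is that 10% is a hard ceiling: it is worded as a target and a listing threshold, and the stopping rule concerns signs or symptoms of CO toxicity. The other is that a donor is likely to be enrolled and to overshoot. The documents give no donor rate, and the lower dose cohorts may sit well away from 10%.

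**Conclusion.** The omission is real, and its direction follows from what COHb measures. Its size is modest and conditional. The proportional increase in the COHb rise is an upper figure, because it assumes none of the donated hemoglobin has been replaced. The 10% target is at risk only at dose levels where non-donors already peak at about 9% or more, and at 110 kg the non-donor peak has to be higher still. At 8% the donor's peak stays near 9% or below. The volumes are assumptions, and the text available is a synopsis.

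This is a low-severity point about who is dosed near the target. It is not a threat to the cohort summaries or to the dose-proportionality analysis.

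**What to change.** Extend exclusion 4 so that the six-week window before first dosing also covers whole-blood donation or comparable blood loss. The sponsor should set the volume threshold. The six weeks are taken over from the transfusion item for consistency and are not derived from hemoglobin recovery, so the sponsor should confirm that the window suits this purpose. In addition, ask subjects not to donate between screening and their last COHb sample, which covers donation after the screening hematology.

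The cost is one line in the eligibility criteria, one screening question and one instruction to subjects. The downside is that a few volunteers are deferred by some weeks. Sample size and planned analyses do not change.
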